The number of patients who have dose reductions, permanent discontinuations or interruptions, and the reasons, will be summarized separately for each of the study drug. The number of patients who have dose re-escalations will also be summarized.

'Dose interrupted' and 'Dose permanently discontinued' fields from the Dosage Administration eCRF pages will be used to determine the dose interruptions and permanent discontinuations, respectively. Dose reductions will be derived programmatically using the dosing information as described below.

The corresponding fields 'Reason for dose change/dose interrupted' and 'Reason for permanent discontinuation' will be used to summarize the reasons.

A dose change is either 'change in prescribed dose level' or 'dosing error' where actual dose administered/total daily dose is different from the prescribed dose.

For the purpose of summarizing interruptions and reasons, in case multiple entries for interruption that are entered on consecutive days with different reasons will be counted as separate interruptions. However, if the reason is the same in this block of entries, then it will be counted as one interruption.

Dose Reduction: Only dose change is collected in the eCRF, the number of reductions will therefore be derived programmatically based on the change and the direction of the change. A dose reduction is a dose change where the prescribed dose level is lower than the previous prescribed dose level or where the actual dose administered/total daily dose is lower than the calculated dose amount based on the prescribed dose. Note that any dose change due to dispensing or dosing error will not be considered a dose reduction. Note also that any previous dose interruptions and any previous dosing or dispensing errors should be ignored when considering whether a subsequent dose change counts as a dose reduction, i.e., if the new dose is lower than the dose prior to any dose interruption or any dose or dispensing error this would still constitute a dose reduction. Missing data: If dose is recorded but regimen is missing or entered as 'none', it is assumed that the investigational drug was taken as per-protocol.

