Dose Re-escalation: For patients with a dose reduction, a dose re-escalation is where the prescribed dose level is higher than the previous prescribed dose level or where the actual dose administered/total daily dose is higher than the calculated dose amount based on the prescribed dose. An increase will only be considered a dose re-escalation if the reason for dose change is "as per protocol". Note also that any previous dose interruptions and any previous dosing or dispensing errors should be ignored when considering whether a subsequent dose change counts as a dose re-escalation.

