For the purpose of summarizing interruptions and reasons, in case multiple entries for interruption that are entered on consecutive days with different reasons will be counted as separate interruptions. However, if the reason is the same in this block of entries, then it will be counted as one interruption.

Dose Reduction: Only dose change is collected in the eCRF, the number of reductions will therefore be derived programmatically based on the change and the direction of the change. A dose reduction is a dose change where the prescribed dose level is lower than the previous prescribed dose level or where the actual dose administered/total daily dose is lower than the calculated dose amount based on the prescribed dose. Note that any dose change due to dispensing or dosing error will not be considered a dose reduction. Note also that any previous dose interruptions and any previous dosing or dispensing errors should be ignored when considering whether a subsequent dose change counts as a dose reduction, i.e., if the new dose is lower than the dose prior to any dose interruption or any dose or dispensing error this would still constitute a dose reduction.

Missing data: If dose is recorded but regimen is missing or entered as 'none', it is assumed that the investigational drug was taken as per-protocol.

Dose Re-escalation: For patients with a dose reduction, a dose re-escalation is where the prescribed dose level is higher than the previous prescribed dose level or where the actual dose administered/total daily dose is higher than the calculated dose amount based on the prescribed dose. An increase will only be considered a dose re-escalation if the reason for dose change is "as per protocol". Note also that any previous dose interruptions and any previous dosing or dispensing errors should be ignored when considering whether a subsequent dose change counts as a dose re-escalation.

2.4.2 **Prior, concomitant, on study and post therapies**

Prior anti-cancer therapy

The analyses performed for the primary analysis can be referred to for details on prior anticancer therapies.

Novartis	Confidential	Page 30
SAP Final CSR LGG		CDRB436G2201

On study Radiotherapy and Surgery

As on study radiotherapy and surgeries are allowed after centrally confirmed radiologic progression of disease or at least a total of 36 months of treatment plus follow-up, whichever comes first. Surgeries and radiotherapies occurring on study will be listed only.

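### Reduction and re-escalation rules compare the dose given with the current prescription, so a return to full dose on an unchanged prescription is never counted

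*SAP*

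**What the plan says.** Section 2.4.1 of the HGG final SAP and of the LGG final SAP carries the same rules. Because the eCRF records only that a dose changed, the direction is worked out by program, so this text is the specification.

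- **Dose change:** "A dose change is either 'change in prescribed dose level' or 'dosing error' where actual dose administered/total daily dose is different from the prescribed dose".
- **Reduction, prescription test:** "A dose reduction is a dose change where the prescribed dose level is lower than the previous prescribed dose level".
- **Reduction, dose-given test:** or "where the actual dose administered/total daily dose is lower than the calculated dose amount based on the prescribed dose".
- **Exclusion:** "Note that any dose change due to dispensing or dosing error will not be considered a dose reduction".
- **Re-escalation, prescription test:** "For patients with a dose reduction, a dose re-escalation is where the prescribed dose level is higher than the previous prescribed dose level".
- **Re-escalation, dose-given test:** or "where the actual dose administered/total daily dose is higher than the calculated dose amount based on the prescribed dose".
- **Re-escalation, reason:** an increase counts only when the recorded reason is 'as per protocol'.

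The dabrafenib worked example (HGG Table 2-7, LGG Table 2-8) has a second record with the prescription unchanged at 125 mg BID, 200 mg/day given, and reason AE. In the third record the prescription rises to 130 mg BID, 260 mg/day is given, and the reason is 'as per protocol'.

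**The concern.** A reduction or re-escalation is a change over time. The prescription test respects that, since it compares successive prescriptions. The dose-given test does not: it compares what was given with what is prescribed in the same record. It can therefore see that a child is below the prescribed dose, but not whether that child has just gone down, gone up or come back.

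When a reduction is entered by lowering the dose given and leaving the prescription alone, two things follow. A full recovery entered the same way satisfies neither re-escalation test. A partial recovery still satisfies the reduction test.

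There is also a clash of wording. The definition of a dose change calls any difference between given and prescribed a dosing error, and dosing errors are excluded from reductions. Yet the dose-given limb of the reduction rule selects exactly those records.

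At stake are the planned counts of reductions with their reasons, and of patients with re-escalations, in both cohorts.

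**Working it through.** **1. The plan's own figures.** Daily totals from the dabrafenib example:

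| Record | Days | Prescribed (mg/day) | Given (mg/day) | Reason |
|---|---|---|---|---|
| 1 | 5 | 250 | 250 | none |
| 2 | 29 | 250 | 200 | AE |
| 3 | 22 | 260 | 260 | as per protocol |

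- Actual cumulative dose: 5 × 250 + 29 × 200 + 22 × 260 = 12770 mg.
- Dose intensity: 12770 / 56 = 228.04 mg/day.
- Relative dose intensity: 12770 / 14000 = 91.2%.

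All three match the SAP. They use the dose given directly and do not depend on the classification rules.

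**2. The rules as tests.** Let P be the prescribed and G the given total daily dose, with subscript 'prev' for the preceding record.

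- Reduction: P < P_prev, or G < P; not if due to an error.
- Re-escalation: a prior reduction, and (P > P_prev or G > P), and reason 'as per protocol'.

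**3. The SAP's example.**

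- Record 2: P = P_prev = 250, so the prescription test is not met. G = 200 < 250, so the dose-given test is met. G also differs from P, so the definition labels the record a dosing error.
- Errors taken from the recorded reason (AE): record 2 is a reduction. Record 3 is then a re-escalation, since 260 > 250. Total: 1 reduction, 1 re-escalation.
- Errors taken from the definition: record 2 is excluded. Record 3 then fails for want of a prior reduction. Total: 0 and 0.

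**4. Return to full dose, prescription unchanged.** Constructed sequence: G = 250, 200 (AE), 250 (as per protocol), with P = 250 throughout. At the third record P > P_prev is 250 > 250, false, and G > P is 250 > 250, false. The result is 0 re-escalations whichever way errors are identified.

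**5. Partial step-up, prescription unchanged.** Constructed sequence: G = 250, 200 (AE), 225, 250, the last two with reason 'as per protocol', P = 250 throughout. At 225, G < P is 225 < 250, true, so with errors taken from the recorded reason the increase counts as a second reduction. At 250 neither re-escalation test is met. The result is 2 reductions and 0 re-escalations, for one step down and two steps up.

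**6. With the dose-given test changed to G against G_prev** (G_prev being the last non-zero, non-error dose given):

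- SAP example: 200 < 250 and 260 > 200, giving 1 reduction and 1 re-escalation. Record 3 meets both limbs and is counted once.
- Full return: 200 < 250 and 250 > 200, giving 1 and 1.
- Step-up: 225 > 200, so the record is no longer a reduction.

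**The case against.** The other side has several good points.

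- **The prescription test works.** It catches record 3 of the dabrafenib example. In the other drug examples the AE reduction is entered by lowering the prescription: trametinib 0.875 to 0.75, carboplatin 175 to 150, vincristine 1.5 to 1.0. None of those reductions needs the dose-given test. A reader might infer that the whole logic uses the wrong comparator, or that the SAP's own example misses a return to full dose. Neither is supported: the fault lies in the dose-given limb, and the example does not contain a return on an unchanged prescription.
- **The exclusion is causal.** It removes changes due to an error, and record 2 gives AE as its reason. If every given-below-prescribed record were an error, the dose-given limb of the reduction rule would never apply, which cannot be intended. A reader might infer that AE-driven reductions drop out of the tables; that rests on the less sensible reading. What remains is that the definition of dosing error says something else, and nothing in the text ties the exclusion to the reason field.
- **The plan looks back to an earlier dose.** For reductions it tells the programmer to skip earlier interruptions and errors when judging the next change, and explains this by reference to the dose before the interruption or error. That clause only skips records. The re-escalation paragraph has the same skip without that explanation, and it does not repair step 4.
- **Other outputs cover the ground.** AEs leading to dose interruption or adjustment are tabulated separately, and all doses with change reasons are listed per patient. This limits the harm but does not correct the counts.

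**Conclusion.** The point holds for the dose-given limb in both final SAPs. Where a reduction and the later return to full dose are both entered on an unchanged prescription, and the return carries the reason 'as per protocol', the re-escalation count is 0 where it should be 1, on any reading of the text. A partial step-up entered the same way is open to being counted as a further reduction. That inflates the number of reductions and the tally by reason; it does not change whether the patient is counted as having had one. The dosing-error definition is a lesser matter: reading it by recorded reason resolves it, but that reading should be written down.

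The effect is confined to descriptive counts. Cumulative dose, dose intensity, relative dose intensity, AE tables, dose listings and efficacy are unaffected.

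The share of patients recorded this way is not in the documents. It could be none, or as much as every patient whose reduction was entered without a change of prescription. The sequences in steps 4 and 5 of the working are constructed; only the reduction half of them appears in the SAP. The documents therefore do not support saying that the regimen will look better or worse tolerated than it was.

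**What to change.** In section 2.4.1 of both final SAPs:

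1. Identify dosing and dispensing errors from the eCRF reason field only, and remove the statement that any difference between given and prescribed is a dosing error.
2. Keep the prescription test. In both rules, replace the dose-given test with a comparison of the total daily dose given against the last non-zero, non-error total daily dose given. Count a change that meets both tests once.
3. Keep the present conditions that a re-escalation needs a prior reduction and the reason 'as per protocol'.
4. Test the code on the dabrafenib example (expected 1 reduction, 1 re-escalation) and on 250, 200 (AE), 250 (as per protocol) mg/day with the prescription unchanged (expected 1 and 1).

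The cost is a few sentences of SAP text and re-programming of one derivation from dose administration fields already collected. The change concerns how recorded doses are classified; it takes no position on any dosing rule.

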2.4.2 Prior, concomitant, on study and post therapies

Prior anti-cancer therapy

The analyses performed for the primary analysis can be referred to for details on prior anticancer therapies.

On-study radiotherapy and surgery

As on study radiotherapy is allowed after centrally confirmed radiologic progression of disease or at least a total of 36 months of treatment plus follow-up, whichever comes first, surgeries and radiotherapies occurring on study will be listed only.

For patients enrolled in the HGG cohort, anti-cancer surgery is allowed for patients enrolled on the study after at least 8 months on treatment or after radiologic progression of disease has been confirmed by investigator. Study treatment may be taken up to one day prior to surgery as deemed appropriate by the investigator.

Post treatment anti-cancer therapy

Anti-neoplastic therapies since discontinuation of study treatment will be listed and summarized by World Health Organization (WHO) Anatomical Therapeutic Chemical (ATC) classification system, PT, and by means of frequency counts and percentages using FAS. In addition, listings will include best response to the regimen. Anti-neoplastic medications will be coded using the WHO Drug Dictionary (WHO-DD).

Concomitant medications

Concomitant therapy is defined as all interventions (therapeutic treatments and procedures) other than the study treatment administered to a patient coinciding with the study treatment period. Concomitant therapy include medications (other than study drugs) starting on or after the start date of study treatment or medications starting prior to the start date of study treatment and continuing after the start date of study treatment.

Concomitant medications will be coded using the WHO Drug Reference Listing (DRL) dictionary that employs the ATC classification system and summarized by lowest ATC class and PT using frequency counts and percentages. Surgical and medical procedures will be coded using MedDRA and summarized by SOC and PT. These summaries will include:

1. Medications starting on or after the start of study treatment but no later than 30 days after start of last dose of study treatment and

Novartis	Confidential	Page 23
SAP Final Analysis HGG		CDRB436G2201

2. Medications starting prior to start of study treatment and continuing after the start of study treatment.

Non-drug therapies and procedures starting after the start of study treatment will also be summarized by SOC and PT.

All concomitant therapies will be listed. Any concomitant therapies starting and ending prior to the start of study treatment or starting more than 30 days after the last date of study treatment will be flagged in the listing. The safety set will be used for all concomitant medication tables and listings.

Systemic corticosteroid use (flagged using a pre-specified list from the clinical team) will be listed and summarized by lowest ATC class and PT using frequency count and percentages. The total daily dose of systemic corticosteroids can be calculated from the dose per administration and the dose frequency (see Section 5.3). Any corticosteroid use starting and ending prior to the start of study treatment or starting more than 30 days after the last date of study treatment will be flagged in the listing.

Concomitant medications that have the potential to impact some specific analyses (e.g. efficacy or safety analyses) will be identified prior to database lock. Separate summaries of these concomitant medications will be produced using the appropriate analysis set (e.g. FAS for those potentially affecting efficacy. According to the study protocol, treatment with substances which are strong inhibitors, or inducers of CYP3A4/5 and CYP2C8, or antiretrovirals or herbal medicines or other anti-cancer or anti-investigational drugs should be avoided. However, some patients may take these substances during the treatment period so these concomitant medications will be selected via programming and tabulated and listed in the CSR. Treatment with the prohibited substances mentioned above will be identified in the database as protocol deviations.

2.5 Analysis of the primary objective

The primary objective is to demonstrate the antitumor activity of dabrafenib in combination with trametinib as measured by ORR to study treatment by central independent review assessment using RANO criteria, in children and adolescent patients with BRAF V600 mutation positive relapsed or refractory HGG.

2.5.1 **Primary endpoint**

ORR is defined as the proportion of patients with best overall response (BOR) of confirmed complete response (CR) or partial response (PR) according to RANO criteria (see Appendix 3 of the study protocol). ORR will be calculated based on the FAS using central independent review of tumor assessment data. Only tumor assessments performed before the start of any further antineoplastic therapy (i.e. any additional secondary antineoplastic therapy or surgery) will be considered in the assessment of BOR. See Section 5.6 for primary estimand definition.

Best overall response

The BOR will be assessed based on reported responses across all evaluation time points. Both CR and PR must be confirmed by repeat assessments performed not less than 4 weeks after the criteria for response are first met. The next scheduled assessment may be used for purposes of

confirmation of response. In the absence of a confirming scan 4 weeks later, this response will be considered only stable disease (SD).

BOR for each patient is determined from the sequence of overall responses according to the following rules, up to progression:

- CR = at least two determinations of CR at least 4 weeks apart before progression
- PR = at least two determinations of PR or better at least 4 weeks apart before progression (and not qualifying for a CR)
- SD = requires at least one SD assessment (or better) determined at or beyond the second regularly scheduled tumor assessment (nominally week 16 i.e >= 105 days allowing for the ±1 week visit window) after start of study treatment (and not qualifying for CR or PR).
- PD = progression after start of study treatment (and not qualifying for CR, PR or SD).
- UNK = all other cases (i.e. not qualifying for confirmed CR or PR and without SD at or beyond the second regularly scheduled post-baseline tumor assessment or progression)

If a patient receives any further anti-neoplastic therapy while on study, any subsequent assessments will be excluded from the BOR determination. Further anti-neoplastic therapies will be identified via protocol deviations or from the data collected on 'Anti-neoplastic therapies since last date of study drug' as appropriate.

2.5.2 Statistical hypothesis, model, and method of analysis

The primary analysis will be performed on the FAS. Point estimate and two-sided exact binomial exact 95% and 80% confidence intervals (CIs) [Clopper CJ and Pearson ES. (1934) The use of confidence or fiducial limits illustrated in the case of the binomial. Biometrical, 26, 404-413] of ORR will be provided. The analysis performed at the time of final analysis will only be considered descriptive and therefore no hypothesis test will be performed. Handling of missing values/censoring/discontinuations

Patients with unknown or missing BOR will be counted as failures. If there is no baseline tumor assessment, all post-baseline overall lesion responses are expected to be 'Unknown'. If no valid post-baseline tumor assessments are available, the BOR must be "Unknown" unless progression is reported. For the computation of ORR, these patients will be included in the FAS and will be counted as 'failures'.

2.5.3 Supportive analyses

As sensitivity analysis, ORR will be calculated and summarized for patients from the Evaluable Set. ORR will be summarized using descriptive statistics (N, %) along with two-sided exact binomial 95% and 80% CIs [Clopper CJ and Pearson ES. (1934) The use of confidence or fiducial limits illustrated in the case of the binomial. Biometrical, 26, 404-413].

New anticancer therapy sensitivity analysis for ORR

The analyses of ORR will be repeated using a stricter ITT approach i.e. including all response assessments irrespective of new anti-neoplastic therapy using the FAS. This analysis will only be performed if data permits.

Novartis	Confidential	Page 25
SAP Final Analysis HGG		CDRB436G2201

Response evaluations recorded after the initiation of new anti-neoplastic therapy will be included in sensitivity analysis of ORR, (i.e. the occurrence of new anti-neoplastic therapy will be ignored for the analyses). The sensitivity analyses will be performed based on both the investigator and independent review assessments using the FAS. In the summary tables, this approach is referred as 'new anticancer therapy ORR sensitivity analysis'.

Concordance analysis of ORR

An assessment of the concordance between central independent reviewer assessment and local investigator assessment of the BOR for each patient will be provided. The calculation will be based on the percent agreement (the proportion of response outcomes that agree or match across both independent reviewer and investigator assessments).

Reasons for "Unknown" BOR

Patients with 'unknown' BOR will be summarized by reason for having unknown status. The following reasons will be used:

- No valid post-baseline assessment
- All post-baseline assessments have overall lesion response UNK
- New anti-neoplastic therapy started before first post-baseline assessment
- SD and/or unconfirmed CR/PR only occurring prior to week 16 visit

